The complete schedule of assessments taken at each Appointment are outlined in Table 1 and described in detail below. Additional details regarding sample ascertainment, marijuana edible selection procedures, power analyses, and the analytic plan follow.

Table 1. Schedule of assessments.		
Assessment	Includes	Time to Complete
1. Orientation Assessments:	- Description of study procedures and measures	
ASAP after screening	- Informed consent; Eligibility re-screening	~0.5 hour
[Part of Baseline Appointment]	- Edible product selection	

2. Baseline Assessments: Same day as orientation [Part of Baseline Appointment]	
 
Pregnancy test, Blood Alcohol Content, Toxicology drug screen
 
Self-report of pain intensity & interference
 
Questionnaires on health behavior, substance use, and psychological measures
 
Inflammation and cannabinoid blood draw
 
Motor and Cognitive battery
 
Wearable device distributed
 
	~1.5 hours
3. Daily Follow-up Assessments: 1x/day for 2 weeks of ad libitum edible use Between Baseline and 2-Week Appointment	- Daily online message report on pain management, marijuana use (if used: amount, strain, method), and sleep; individually tailored links	~2-5 mins/day
4. 2-Week Mobile Assessments: Before, 1, and 2 hours after self-administration 2-weeks after Baseline Appointment	- All Baseline measures (wearable device collected) - Additional surveys on Impact of Marijuana	~3 hours
5. Monthly Follow-up Assessments: 1x/month for six months After 2-Week Appointment	- Monthly online survey; individually tailored links	~10-15 mins/month
Total time (6.5 months)	Participants paid \$220	~6.5 hours

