# Marijuana Administration at Home

The proposed work will utilize a design that is observational and does not involve assignment by the research team. More specifically, patients who are already planning to try marijuana as a treatment for their pain will choose their own product at baseline and inform staff of their choice. The patient will then purchase the product at a dispensary. The patient will be observed before they purchase and begin using their product (Baseline Appointment), during use (Daily follow-up messages), and after 2-weeks (2-Week Appointment) of using their product ad libitum at home. After the 2-Week Appointment, we will complete Monthly follow-up surveys with the patient for 6 months to determine what additional products the patient may have tried and to collect self-report information on product use and current levels of pain.

Specifically, at the end of the Baseline Appointment, individuals will be asked to select and purchase an edible marijuana product to use ad libitum for the next 2 weeks. Colorado requires all edibles to be tested by a state lab, which allows us to have a precise measure of potency after the participants purchase their products. Importantly, the researchers who conduct the assessments as well as all the senior investigators will be blind to the participant's product choice. Participants will use their selected product at home consistent with the packaging directions, direction from their physician, or as they see fit, and will be asked not to use any other marijuana product during the 14 days before their 2-Week Appointment (with one Pre- and two Post-administration mobile assessments on the final day of the 2-week ad libitum study period). Study staff will not provide any directions regarding dosing and administration.

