## **Baseline Appointment Procedure and Assessments**

Subjects who meet inclusion criteria (see Table 2 above) will be scheduled for a Baseline Appointment and given instructions, including not consuming alcohol for 24 hours, tobbacco, caffeine, and any other drugs for 72 hours (excluding those needed for regular pain management) prior to the appointment. Subjects will be reminded to eat a small meal and hydrate well before the baseline appointment. After arriving at the CUChange Laboratory, each subject will go through the consent process and after all questions have been answered and if participants consent, Baseline procedures will begin (see Table 3). A urine toxicology and a pregancy test (for females) will also be administered to verify if subjects have recently taken illicit drugs and to ensure that they are not pregnant. A blood draw will be taken to quantify current use of cannabinoids and inflammatory markers (1st of 4 total blood draws completed during the entire study). All blood draw procedures performed during this study will involve collecting venous blood (40 mL per draw) with venipuncture of a peripheral arm vein using standard, sterile phlebotomy techniques. Subjects will then complete current and historical health and substance use assessments (see section below and Table 3 for details), and a motor and cognitive testing battery.

At the end of the Baseline Appointment, individuals will be asked to self-select an edible marijuana product based on their preference. Participants will then use their selected product at home, consistent with the packaging directions, direction from their physician, or as they see fit, and will be asked not to use any other marijuana product during the 2-Week study period, before their 2-Week Appointment

(Mobile Laboratory assessment). Study staff will not provide any directions regarding dosing and self-administration. While participants themselves will not be blind to their product choice, importantly, the researchers who conduct the assessments as well as most of the senior investigators will be blind to their selection. At the Baseline Appointment, participants will be given instructions and allowed to practice responding to an online daily message prompt (described below), that will commence after they purchase an edible of choice.

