Marijuana Purchase Task (MPT)	The marijuana purchase task (MPT) is a valid measure of the	
	relative economic value of marijuana is needed to characterize	
	individual variation in the drug's reinforcing value. This asks participants to estimate the number of marijuana joints they	
	would purchase at increasing prices and can be used to	
	examine the associations between marijuana use and MPT	
	demand indices.	
*Cannabis	This modified version details the primary reasons, frequency,	
Questionnaire/Marijuana Users	and type of cannabis use patterns in occasional and regular	
Health Cohort/ (MUHC)	users.	
*Impact of Marijuana on Pain	This modified short self-report questionnaire on the impact of	
(IMP)	marijuana on pain and health compared to other types of pain	
	management (e.g., drugs, opioids, exercise) and the expected	
	and past risks and benefits (e.g., sleep, mood, anxiety).	
Health Related Quality of Life	This is a Short Form 12 Health Survey, which consists of 12	
(HRQL)	questions across eight health domains and is sensitive in	

	detecting changes in time (one month) in health-related quality	
*Timeline Follow-Back (TLFB)	of life.  TLFB is used to assess daily substance use (for the 2 weeks prior to the Baseline Appointment, and 2 weeks prior to the Mobile Appointment. Our modified TLFB procedure will estimate both frequency of marijuana use and amount used per day, using visual stimuli as well as the method of administration 77,78.	
Blood Alcohol Content (BAC)	Breathalyzer test for recent alcohol consumption.	
Physiological Weight Scale	A digital scale will be used to collect subject weight at each inperson appointment.	
Stadiometer	A ruler with a sliding horizontal headpiece will be used to collect subject height at the Baseline Appointment.	
Pittsburg Sleep Quality Index (PSQI)	Measurement of the quality and patterns of sleep from poor to good measuring seven domains (e.g., latency, duration, disturbances) over the last 2 weeks.	
*Roland Morris Disability Questionnaire (RMDQ)	This asks participants about how their experience of low back pain interfered with or affected their enjoyment of various daily activities in the past 2-weeks (modified from today). This 24-item self-report asks participants to mark an item if they experienced each type of pain interference, each mark is scored as 1 point, with a total range from 0-24, higher scores demark higher interference.	

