*Profile of Mood States (POMS)	The modified Profile of Mood States (POMS) will be used to collect baseline information on mood as well as information on mood changes throughout the study  .	
Functional Assessment of Cancer Therapy-Cognitive Function (FACT-Cog)	A subjective measure of perceived cognitive impairments, ability, as it impacts others, and quality or life.	
Patient Global Impression of Change (PGIC)	The Patient Global Impression of Change (PGIC) scale is a subjective measure consisting of 1 question to ask participants any changes in their overall status of pain in the past two weeks.	
Baseline Appointment (CINC Lab)	Informed consent & study orientation; BAC test; Urine toxicology and Pregnancy test; Heart rate; Pain Intensity & Interference ratings; 1 st Blood draw; Questionnaires; Cognitive & Motor Battery; Wearable distributed; Appointment 2 scheduling; Monetary Compensation.	120 minutes
Daily Follow-Up Messages	Respond to brief questions (online) about marijuana use, sleep quality, and pain management once per day for 2 weeks after self-directed edible use. Each survey has a 24 hour window before the link expires.	2-5 mins/day x 14 days (~30 mins total)
2-Week Appointment (Mobile Lab) -Pre-administration	Immediately before edible self-administration; Come out to Mobile laboratory; Heart rate; Pain Intensity & Interference ratings; 2 nd Blood draw; Questionnaires; Cognitive & Motor Battery; Return home to self-administer edible.	75 mins
-Post 1-hr administration	1 hour after edible self-administration; Return to Mobile laboratory; Heart rate; Pain Intensity ratings; 3 rd Blood draw; Questionnaires; Cognitive & Motor Battery; Return home.	45 mins
-Post 2-hr administration	2 hours after edible self-administration: Return to Mobile laboratory; Heart rate; Pain Intensity ratings; 4 th Blood draw; Questionnaires; Cognitive & Motor Battery; Return wearable; Debriefing; Monetary Compensation; Return home.	60 mins
Monthly Follow-up Surveys	Respond to brief questions (online) about marijuana use, sleep quality, and pain management once per month for 6 months, Monetary compensation (each month). Each survey has a 2 week window before link expires.	10-15 mins/month x 6 months (~60 mins total)
TOTAL STUDY DURATION (6.5 months)		~6.5 hours

**Key:** \*=use of a modified measure

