*Protocol Deviations:* This study is observational in nature, entails multiple exploratory time points and analysis, and asks for a large amount of self-initiated and voluntary participation for each task, with no

previously defined or investigated expected norms or minimum standards for completion. Therefore, if participants decide to not complete a particular assessment(s) they will not be considered a protocol deviation (i.e., if they elect to not answer or complete parts of the Baseline or 2-Week appointment or any/all of the daily or monthly exploratory surveys). However, we will record and account for any missing data in our data analysis (as noted in Section IV Research Study Design – Statistical Analysis Plan). Importantly, our lab has had little difficulty completing all or nearly all of the proposed assessments in ongoing or previous longitudinal studies, scheduling and maintaining similar appointment criteria (i.e., scheduling follow-up visits within a set time window), and collecting multiple blood samples on different visits or within the same visit.

While we do not anticipate deviations from the above procedures, to increased replicability and efficiency of future studies, we will define and record the following events as they may impact the primary outcomes of the study. Therefore, a protocol deviation will be noted (unless missed due only to participant refusal) if:

- 1) A 2-Week Mobile Lab appointments is not completed within 2 weeks (14 days)  $\pm$  4 days from the Baseline appointment (i.e., 2-Week appointment should be  $\pm$ 4 days from the intended 14-day study period), and/or
- 2) A blood sample collection is not obtained from the Baseline appointment, and/or 2 or more blood sample collections are not obtained from the 2-Week Mobile Lab appointment.
- 3) An assessment is not administered to the subject due to unforeseeable events (i.e. REDCap system malfunction).

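### The 2-Week visit is counted from Baseline in the operative rule but from product use elsewhere, so a compliant day-10 visit has at least 4 of 14 RMDQ recall days before any use

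*Combined protocol and SAP*

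**What the plan says.** Two anchors for the visit stand side by side.

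**Counted from Baseline.** The Protocol Deviations paragraph (Section XII) notes a deviation unless the visit falls within 14 days plus or minus "4 days from the Baseline appointment". Table 1 (Section IV) times it at "2-weeks after Baseline Appointment". The appointment summary closing Table 3 lists "Appointment 2 scheduling" among the Baseline tasks, so the visit is booked before the product is bought.

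**Counted from use.** The overview in Section IV places the visit after the two-week administration period, and the section on administration at home puts it on the last day of that period. The Hypothesis 1 primary analysis treats the Pre-administration RMDQ as following two weeks of use. The deviation rule's own parenthesis speaks of plus or minus "4 days from the intended 14-day study period" without defining when that period starts.

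**Start of use.** Section IV says "The patient will then purchase the product at a dispensary". It also says that "at the end of the Baseline Appointment, individuals will be asked to select and purchase an edible marijuana product", but sets no deadline. Section XII says of the daily messages "that will commence after they purchase an edible of choice", whereas Table 4 fixes them at days 2 to 15, with Baseline on day 1 and the visit on day 16.

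**Recall.** Table 3 describes the RMDQ as asking about interference "in the past 2-weeks (modified from today"). An item is marked if that interference was experienced, and the total runs from 0 to 24.

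**The concern.** The primary outcome is read as pain interference during two weeks of product use. If the visit is timed from Baseline and use starts later, part of the recall describes days before any product was taken, and that part differs between participants. Because an item is marked if the problem occurred in the period, a few pre-use days could count for more than their share of the 14.

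At stake is the Hypothesis 1 coefficient. Recall days that the product could not have affected may weaken the association between blood level and RMDQ. If shorter use also means lower blood levels, the same participants would have low levels and more pre-use interference, which would create an association in the hypothesised direction. No primary model adjusts for time on product. The SAP describes other outcomes over the same two weeks: prior-two-week pain intensity, DASS and the global impression of change.

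**Working it through.** **Plan's own figures.** The plan gives no figure for the share of the recall before use. Its timing figures are the window (14 − 4 = day 10 to 14 + 4 = day 18 after Baseline) and the Table 4 visit (day 16 − day 1 = 15 days after Baseline). Its power figure reproduces: for one coefficient, N = 246 and f² = 0.04, the noncentrality is 0.04 × 246 = 9.84, and power at two-sided 0.05 is 0.878, against the stated 0.88.

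**Inputs.**
- V: days from Baseline to the visit, 10 to 18 (Protocol Deviations) or 15 (Table 4).
- d: days from Baseline to first use. Not given in the documents, so assumed and shown over a range.
- Recall: 14 days (Table 3).

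**Formula.** Pre-use days in the recall = max(0, min(14, 14 − (V − d))); share = that number / 14.

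| Visit day V | d = 0 | d = 1 | d = 2 | d = 3 | d = 4 | d = 7 |
|---|---|---|---|---|---|---|
| 10 | 4 (29%) | 5 (36%) | 6 (43%) | 7 (50%) | 8 (57%) | 11 (79%) |
| 14 | 0 | 1 (7%) | 2 (14%) | 3 (21%) | 4 (29%) | 7 (50%) |
| 15 | 0 | 0 | 1 (7%) | 2 (14%) | 3 (21%) | 6 (43%) |
| 18 | 0 | 0 | 0 | 0 | 0 | 3 (21%) |

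Only the d = 0 column needs no assumed delay. Half the recall is reached when d = V − 7, that is a delay of 3, 7, 8 or 11 days at visits on day 10, 14, 15 or 18.

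**Overlap with Baseline.** At V = 10 the follow-up recall reaches back 14 − 10 = 4 days before Baseline. The Baseline RMDQ, which is the model's covariate, covers those same 4 days.

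**Consistency check.** Section IX pays for up to 14 daily messages at the 2-Week visit, with a bonus for at least 12. At one message a day, no more than about 10 could have been sent by a day-10 visit, so the bonus could not be earned at a visit that the rule allows.

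**Illustration of dilution only.** Suppose every participant had the same pre-use share and the effect shrank in proportion to exposed days. With 4 pre-use days, f² becomes 0.04 × (10/14)² = 0.0204 and power is 0.61. With 7, f² is 0.04 × (7/14)² = 0.01 and power is 0.35. These are not forecasts: visits will spread over the window, and the net direction of the effect is not established.

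**Effect of re-anchoring.** With 14 ± 4 days counted from first use, the earliest visit is day 10 of use, which still leaves 14 − 10 = 4 pre-use days (29%). With a visit no earlier than 14 days after first use, the number is 0.

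**The case against.** The deviation rule sets a tolerance, not the visit date. Several places show that the visit is meant to follow two weeks of use: the overview, the section on administration at home, the payment for 14 daily messages, and the rule's own parenthesis. Participants are asked to buy at the end of Baseline. With prompt purchase the Table 4 grid fits the purchase-triggered messages, and its visit leaves no pre-use days for delays of 0 or 1 day. Use is ad libitum, so non-use days inside the recall are part of the design.

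Most of this stands as evidence of intent, and it limits how often the problem will be large. It does not override a rule under which a day-10 visit is compliant, and no text caps the delay. A non-use day chosen after starting also differs from a day before the product was obtained.

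Three stronger readings are tempting but unsupported.
- That up to half the recall precedes use. This needs the earliest visit and an assumed 3-day delay. It is neither a documented figure nor a maximum.
- That the association is necessarily diluted. The documents do not settle the direction.
- That every primary endpoint is affected through recall. The cytokine and cognitive endpoints have no two-week recall.

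**Conclusion.** The anchor is inconsistent and should be reconciled. From the documents' own figures, a compliant day-10 visit has at least 4 of 14 RMDQ recall days (29%) before any use, overlapping the Baseline recall. Larger shares rest on an assumed delay: half or more at day 10 if first use is 3 or more days late, and 14% at the Table 4 visit with a 3-day delay. The typical share cannot be known, because neither the delay nor the spread of visit days is given.

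The consequence is that exposed time varies between participants in the two-week recall outcomes, with a bias that could go either way. The route to a spurious association assumes that shorter use lowers the Pre-administration blood level, which the documents do not state. For pain intensity the two-week period is the SAP's; the average and worst items in Table 3 cover 7 days, and on that wording pre-use days enter only when first use is fewer than 7 days before the visit.

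The deviation rule only records visits outside the window. Nothing excludes them from the analysis, so the range above is not a bound on the analysed data.

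**What to change.** 1. Reconcile the Section IV overview, Table 1, the Baseline procedures, the Protocol Deviations rule and Table 4 on one anchor: first edible use, with the assessment visit no earlier than 14 days after it. Keeping a tolerance of 4 days on the early side would leave the same 4 of 14 days. This concerns only when the assessment takes place, not how participants use the product.
2. For each participant, derive the number of pre-use days within the 14-day recall. The Timeline Follow-Back covers the two weeks before the mobile visit. The daily messages are needed too, because at visits more than 14 days after Baseline the Follow-Back alone can miss an earlier first use. Messages may be skipped, so state how a missing first-use date is handled.
3. Add a sensitivity analysis of the RMDQ model limited to participants with no pre-use days in the recall, and repeat it for the other two-week outcomes.
4. Days of use as a main-effect covariate is optional. It adjusts the mean RMDQ for duration but does not by itself correct an attenuated blood-level slope.

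The cost is that the visit can no longer be fixed at Baseline, mobile-lab booking moves later for participants who buy late, and the sensitivity analysis has a smaller N. No new data are needed. If enrolment is already complete, steps 2 to 4 can still be specified before the dataset is locked.

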#### XIII. SPECIMEN MANAGEMENT

Blood samples collected in the mobile lab will be kept in an insulated biohazard transport bag. All blood samples collected during the study will be stored in locked freezers within the PI's laboratory designed specifically for storing biological specimens. Samples will be coded with a randomly generated participant ID number and all data collected will be stored on a password protected server and separate from the master list linking the ID numbers to participants' contact information, also stored on a password protected server and only accessible by a research team member. At study closure, all links between participant name and number will be destroyed, at which point the blood specimens will be considered de-identified. After all analyses are complete, these specimens will be destroyed.

#### XIV. DATA MANAGEMENT

Signed consent forms will be stored in a locked filing cabinet in the PI's lab at the CINC. All data from self-report and interview measures will be stored on password protected computers and on the PI's password protected server in the CINC, both of which are only accessible to research staff. All stored data will be recorded from secure survey software. Any identifying information will be destroyed after the last appointment (on-line or in-person), and biological samples will be destroyed after all analyses are complete.

## XV. WITHDRAWAL OF PARTICIPANTS

Situations in which the entire study may be terminated early include the following: If the Principal Investigator or other governing official discovers serious concerns about subjects' safety, inadequate performance or rate of enrollment (this includes a missed study appointment); because study objectives have been obtained according to pre-established statistical guidelines; or in the unlikely event that the Principal Investigator retires and no other additional investigators are able to succeed his role within the

research project. Though highly unlikely, the circumstances under which a participant would be withdrawn without his or her consent include: obviously not following instructions or behavior that is verbally or physically abusive towards research staff. Those who experience early withdrawal will receive prorated payment based on the number of appointments that they completed.

# XVI. RISKS TO PARTICIPANTS

## Risks Pertaining to the Legality of Cannabis

The possession and use of cannabis is legal at the state level, but illegal at the federal level. Any risk associated with this study is not greater than risks experienced by participants when they purchase cannabis outside of the study. We will comply with all NIH guidelines, and a Certificate of Confidentiality will be deemed applicable for our study, decreasing the risk for participants.

